3.1.2 Exclusion Criteria

- Patients with hearing impairment;
- Patients previously diagnosed with psychiatric disorders: schizophrenia.

3.2 Experimental Design This is a prospective open-label randomized study evaluating the practice of yoga and gentle massage combined with standard treatment versus the use of standard treatment alone.

3.3 Sample Size The sample will consist of a total of 40 patients for this study. Based on a pilot sample (N = 40) with only one session of yoga + gentle massage, an improvement of 1.58 points (SD = 1.58 points) in fatigue was observed. Aiming to find an average difference of at least 1.5 points between the intervention group (yoga + gentle massage + standard treatment) and the control group (exclusive standard treatment) over 8 proposed sessions, with 80% power and 95% confidence, a sample of 18 patients in each group would be required. Since, in addition to fatigue, other parameters such as pain, nausea, anxiety, and well-being will be evaluated, we will use a sample of at least 20 patients per group to also account for these parameters, totaling at least 40 patients in the study.

3.4 Randomization Randomization will be performed according to the randomization block generated by Excel and will be carried out using the REDCap tool. Thus, upon accepting participation in the protocol, each patient will receive an individual number that will be included in this randomization block, with the sequence of their participation in the protocol predetermined by the Excel table to be inserted into REDCap and randomized according to parameterization, stratified by age groups: 18 to 30 / 31 to 50 / 51 to 65 / over 66 years 18 to 40 / 41 to 60 / above 61 years and by type of transplant: autologous, allogeneic, and umbilical cord.

3.5 Training Program During the HSCT period, patients will be randomized into two groups:

- Group A (control): standard treatment
- Group B (intervention): yoga or gentle massage plus standard treatment

The intervention sessions will be verbally conducted by integrative therapists from the Integrative Medicine Team, hired by the Oncology and Hematology Center of HIAE, all with

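### Nine or twelve randomisation strata are too many for 40 patients: 20 per group is usually missed from a total of 40, although the cost in power is small

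*Protocol*

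**What the plan says.** Section 3.4 of the Protocol describes blocked allocation ("Randomization will be performed according to the randomization block generated by Excel") without giving a block size. It stratifies by age and transplant type. Two age lists follow one another with nothing to say which applies: "18 to 30 / 31 to 50 / 51 to 65 / over 66 years" and then "18 to 40 / 41 to 60 / above 61 years". The second list runs straight on into the second factor, which has three levels: "above 61 years and by type of transplant: autologous, allogeneic, and umbilical cord".

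Section 3.3 opens with a fixed size, "The sample will consist of a total of 40 patients for this study". It calculates that "a sample of 18 patients in each group would be required", and then raises this because four further symptoms are to be assessed: "we will use a sample of at least 20 patients per group to also account for these parameters". The same sentence ends with a total of at least 40, so 40 is a fixed number in one place and a minimum in another.

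Section 3.7 compares group means by Student t or Mann-Whitney tests. It mentions neither the strata nor any covariate.

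**The concern.** Permuted blocks balance the arms only where blocks are completed. With about 3 to 4 patients per cell, most cells can end part-way through a block, and the leftover imbalances add up across cells. The grid can therefore balance the arms less well overall than a much simpler scheme would. Two things are at stake: whether 20 per group really follows from the design, and whether the analysis matches the way patients were allocated. The allocation table is built before enrolment, so a later analysis document cannot repair the first of these.

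**Working it through.** **The plan's own sample size.** Inputs from section 3.3: difference 1.5, SD 1.58, power 80%, 95% confidence (two-sided 5%).

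n per group = 2 × (1.960 + 0.842)² × (1.58/1.5)² = 2 × 7.849 × 1.1095 = 17.4, so 18. The stated figure is reproduced. With the exact noncentral t, 18 per group gives 79.0%, 19 gives 81.3% and 20 gives 83.3%.

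**Number of cells.**
- Three-level age list: 3 × 3 = 9 cells; 40/9 = 4.4 patients per cell.
- Four-level age list: 4 × 3 = 12 cells; 40/12 = 3.3 patients per cell.

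**Arm balance.** The protocol gives neither patient mix nor block size, so these are assumptions:
- transplant type 50% autologous, 45% allogeneic, 5% cord;
- age 25/40/35% (three levels) or 10/30/40/20% (four levels);
- block sizes 2, 4, 6 and 8.

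On this mix cord contributes 0.05 × 40 = 2 patients, spread over three or four cells. The comparator has two strata: autologous, and any donor graft including cord. Simulated permuted blocks give:

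| | 9 or 12 cells | 2 strata |
|---|---|---|
| Exact 20:20 split | about 20-38% | 48-76% |
| Smaller arm 18 or fewer | about 11-41% | 0-7% |

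The better end of each range belongs to blocks of 2 and the worse end to blocks of 8. Repeat runs move these figures by a point or two. Over a wider set of five age mixes and four transplant mixes, 20:20 was missed in 51-82% of simulated trials.

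**Cost for the planned unadjusted test.** The noncentrality is 1.5 / (1.58 × √(1/n₁ + 1/n₂)). For 20:20 it is 1.5 / (1.58 × √0.1000) = 3.00; for 22:18 it is 1.5 / (1.58 × √0.1010) = 2.99.

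| Split | 20:20 | 21:19 | 22:18 | 23:17 | 24:16 | 25:15 |
|---|---|---|---|---|---|---|
| Power | 83.3% | 83.2% | 82.9% | 82.5% | 81.8% | 80.9% |

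Averaged over the simulated allocations, power is about 83% for every grid and block size.

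**Cost for adjusted analyses, strata not prognostic.** Adding age group and transplant type as separate factors gives about 80-82%. With one indicator per crossed cell, the information is Σ n₁ⱼn₂ⱼ/nⱼ over cells, compared with 10 for an unstratified 20:20 split:

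| Block size | 9 cells | 12 cells |
|---|---|---|
| 2 | 81.3% | 80.2% |
| 4 | 80.6% | 78.9% |
| 6 | 80.0% | 78.0% |
| 8 | 79.5% | 77.1% |

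With two strata the figure is about 83%.

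**If the strata are prognostic.** Take illustrative information of 9.2 (9 cells) and 8.5 (12 cells). Power is 79.6% and 76.1% when the strata explain nothing. It rises to 83.6% and 80.3% when they explain 10% of the variance.

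**The case against.** The strongest reply is that the planned analysis barely notices. Section 3.7 uses unadjusted tests, a 21:19 or 22:18 split costs under half a percentage point, and the calculated need is 18 per group rather than 20. That stands, and it limits the point to arm balance and consistency.

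A reader might infer more than the documents support:
- **That stratification leaves the trial underpowered.** It does not. Power falls clearly below 80% only with 12 cells, blocks of 4 or more, one indicator per cell and non-prognostic strata. The protocol plans no such model. Section 1.2 names younger age among factors associated with fatigue, so the last assumption may also be pessimistic.
- **That many blocks never fill.** This holds for blocks of 4 or more. With blocks of 2, only 0.1 to 1.8 strata on average fail to complete one, and the block size is not stated. Blocks of 2 do not rescue the 20:20 target, however, and in an open-label study they make every second allocation within a stratum predictable.
- **That patients in one-arm cells are wasted.** This is true only of a model with one indicator per cell.

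It can also be said that a minimum of 20 per group and of 40 in total allows recruitment past 40. That reading is open, but it conflicts with the fixed total at the start of section 3.3. Lastly, two-level transplant type is one remedy among several; two age levels or minimisation would also serve.

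**Conclusion.** The point holds as a modest design weakness. The 9 or 12 cells and the two conflicting age lists follow from the text alone. Under the assumed mix and blocks of 2 to 8, an exact 20:20 split from 40 patients occurs in roughly 20-38% of trials, about half as often as with two strata or less. The per-group figure in section 3.3 is therefore not something the scheme in section 3.4 delivers. The power consequence is small: about 83% for the planned test, 80-82% with additive adjustment, and a drop to about 80% (9 cells) or 77-80% (12 cells) only with one indicator per cell. At worst this uses up the margin gained by going from 18 to 20 per group and a little more. The percentages depend on the assumed mix and block size; the direction held across all the mixes tried.

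**What to change.** - **Section 3.4:** reconcile the age lists and reduce the strata, for example to transplant type at two levels (autologous; any donor graft including cord) with permuted blocks. If age groups stay, close the boundaries too: as printed, age 66 in the first list and age 61 in the second belong to no group.
- **Section 3.7:** replace the unadjusted comparison with one adjusted for two-level transplant type and continuous age. Section 3.1 already collects both. The cost is under 1.5 points of power even if neither factor is prognostic, and there is a gain if they are.
- **Section 3.3:** either state about 20 per group, or let recruitment continue until both arms reach 20, and make the total agree.
- **If enrolment has started:** keep the existing allocation list, record which age list it used, and make only the analysis change, without adjusting for the 9 or 12 cells.

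The cost is a new Excel/REDCap allocation table and a few amended sentences. The one downside is that age is then balanced only by chance, which the covariate handles.

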postgraduate degrees in Yoga (Institute of Teaching and Research in Yoga - IEPY) and in Integrative Health Bases and Well-being (Albert Einstein Institute of Teaching and Research - IIEP). Group B (intervention) will receive a total of 8 individual integrative practice sessions at the bedside, each lasting 15 to 20 minutes, with 2 sessions per week during the following periods: • from admission until Day 0 • until Day 7 • until Day 14 • until Day 21 or discharge. The therapist will choose the integrative practices that best suit the patient for each session, according to their psychophysical state and presented symptoms, as there are many variations during HSCT. Group A (control) will receive 8 visits from integrative therapists who will remain in the patient's room, able to interact but without offering integrative practices, during the same period described above. After Day 21, these patients will also receive 8 integrative practice sessions at the bedside or in the Integrative Medicine room. If any patient from this group needs to receive Integrative Medicine care, they will receive it and be withdrawn from the study.

3.5.1 Yoga Yoga sessions will be conducted at the patient's bedside, in a supine or sitting position, using one or more of the following techniques: gentle stretches (asanas), guided relaxation (savasana), deep and slow diaphragmatic breathing (pranayama), and meditative exercises focusing on natural breathing or visualizing a place that brings well-being (dhyana). Based on these techniques, the integrative therapist will choose what best suits the patient for each session, according to their psychophysical state and presented symptoms, as there are many variations during HSCT. Non-violence (ahimsa) as a basic and essential principle of yoga practice will be reiterated in each class to encourage participants to be gentle with themselves and accept possible limitations.

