3.5.2 Massage Gentle massage involves gentle touches, using light pressure, mainly with the palm, with a slow and steady rhythm over the entire body. It can be performed over clothing and even over the sheet and blanket. The sequence of light touches begins at the head, moving down the right shoulder, arm, forearm, and right hand; thigh, knee, leg down to the right foot, where it will be gently massaged on the back, fingers, and sole of the right foot. Afterward, the therapist's hands move up in the reverse sequence on the left side of the patient's body, finishing again at the head. The action of this technique is on the skin and not on the muscles. Sensory information from this gentle touch on the epidermis activates the Relaxation Response in the Autonomic Nervous System, increasing the stimulation of the PNS and decreasing the excitement of the SNS.

3.6 Assessments The scales and questionnaires will be digitally administered through the REDCap Einstein platform. Only the Qualitative Report will be provided in printed form for the patient to describe their experience. All these documents are available in the appendices of this project.

3.6.1 Edmonton Symptom Assessment Scale - ESAS-Br The Edmonton Symptom Assessment Scale - ESAS-Br will be used before and after each of the 8 sessions in both groups, assessing the domains: pain, fatigue, nausea, anxiety, and well-being.

3.6.2 Functional Assessment Cancer Therapy - Bone Marrow Transplantation Quality of Life Scale - FACIT-BMT The Functional Assessment Cancer Therapy - Bone Marrow Transplantation Quality of Life Scale - FACIT-BMT will be used at two time points: upon admission and on Day 21 (or at discharge).

3.6.3 Duke Religious Index - DUREL The Duke Religious Index - DUREL will be applied at two time points: upon admission and on Day 21 (or at discharge).

3.6.4 Qualitative Report The Qualitative Report will be handed to the patient in printed form on Day 21 (or at discharge), using an open-ended question for the patient to describe: "What was your experience with Integrative Medicine like?"

3.6.5 Patient-Reported Experience Measures (PREMs) To assess patient satisfaction and experience, the Patient-Reported Experience Measures (PREMs) will be applied on Day 21 (or at discharge).

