3.7 Statistical Analysis The qualitative characteristics of patients will be described according to groups using absolute and relative frequencies, and associations with the groups will be verified using chi-square tests or exact tests, while quantitative characteristics will be described according to groups using summary measures (mean, standard deviation, median, minimum, and maximum), and group comparisons will be made using t-Student tests or Mann-Whitney tests depending on the probability distribution of the data. Mean changes in each ESAS domain over the 8 therapy sessions will be calculated, and group means on the scales will be compared using t-Student tests or Mann-Whitney tests. The analyses will be performed using IBM-SPSS software for Windows version 22.0, tabulated using Microsoft-Excel 2010 software, and tests will be conducted at a 5% significance level.

4. ETHICAL ASPECTS This project will be submitted for review to the Research Project Management System of the Albert Einstein Israelite Hospital (HIAE), the institution hosting the Einstein Family Dayan - Daycoval Oncology and Hematology Center. Subsequently, it will be submitted to the Brazil Platform and the institutional Research Ethics Committee. All patients will sign the Informed Consent Form because it involves human subjects.

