5. RISKS AND BENEFITS

5.1 Risks The expected risks, if any, for the procedures of this study (yoga and gentle massage) and for responses to research questions are minimal. Given that the topic of integrative practices would not put subjects at risk of health, criminal or civil liability, or be detrimental to their financial situation, employability, educational advancement, or reputation. Although we consider the risks of participation in this study to be low, we will ensure that any situation is handled sensitively and empathetically. If any discomfort arises during the study, it may be discontinued.

5.2 Benefits As this is a randomized study, participants may not directly benefit from the proposed research; however, others may benefit from the knowledge gained in this study.

REFERENCES

1. Squarisi D. Desafios: relatos de celebração à vida. Inbook Editora; 2017.
3. Alois Gratwohl; Helen Baldomero; Mahmoud Aljurf; et al. Hematopoietic stem cell transplantation A Global Perspective. *Jama*. 2010;303(16):1617–24.
5. ABRALE Transplante de Medula Óssea [Internet]. [cited 2021 Nov 29]. Available from: <https://www.abrale.org.br/informacoes/tratamentos/transplante-de-medula-ossea/?q=tmo/tipos>
7. [name], RN, FAAN, Cathy L. Rozmus, DSN, RN, Tito R. Mendoza P, [name], [name], MS, AOCN, [name], DrPH M, [name], [name], and Charles S. Cleeland P. Symptoms and Quality of Life in

Diverse Patients Undergoing Hematopoietic Stem Cell Transplantation. *J Pain Symptom Manag.* 2012;44(2):168–80.

8. Deng G. Integrative Medicine Therapies for Pain Management in Cancer Patients. *Cancer J.* 2019;25(5):343–8.

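### Control patients who need Integrative Medicine care leave the study, Group B has no such exit, and their remaining assessments are never collected

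*Protocol*

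**What the plan says.** Section 3.5 describes the control arm in three sentences. Controls are visited on the same schedule as the intervention arm: "Group A (control) will receive 8 visits from integrative therapists who will remain in the patient's room, able to interact but without offering integrative practices". They are offered the practices later: "After Day 21, these patients will also receive 8 integrative practice sessions at the bedside or in the Integrative Medicine room". Then comes the rule at issue: "If any patient from this group needs to receive Integrative Medicine care, they will receive it and be withdrawn from the study". The group meant is Group A, and the rule matters before Day 21, because after that every control is offered the practices anyway.

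For Group B the protocol adapts the session instead: "The therapist will choose the integrative practices that best suit the patient for each session, according to their psychophysical state and presented symptoms". The only other stopping text is in section 5.1: "If any discomfort arises during the study, it may be discontinued". It names neither group and does not depend on a need for the tested care.

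On data collection, section 3.6.1 says the ESAS "will be used before and after each of the 8 sessions in both groups". FACIT-BMT and DUREL are taken at admission and at Day 21 or discharge (3.6.2, 3.6.3). PREMs and the open question are taken at Day 21 or discharge only (3.6.4, 3.6.5). Section 3.7 states: "Mean changes in each ESAS domain over the 8 therapy sessions will be calculated", with groups compared by t-test or Mann-Whitney test.

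**The concern.** The sentence ties together two separate things: a control receiving the care, and that control leaving the study. The first is a clinical matter and is not questioned here. The second removes a randomised patient from follow-up because of an event after randomisation, in one arm only. The trigger is not defined. It is a need for the tested type of care, in an open-label trial with symptom outcomes, so a link with symptoms is plausible, although that is an inference.

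The controls still present at Day 21 may then be a selected subset, and neither test in section 3.7 corrects for that. The protocol also does not say whether ESAS pairs taken before withdrawal are kept. The direction of any bias is not fixed: need may follow the level of symptoms, while the ESAS outcome is change across a visit.

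**Working it through.** **Inputs from the protocol (3.3, 3.7).** Difference 1.5 points, SD 1.58, 80% power, 5% level (taken as two-sided), 18 per group required, at least 20 per group planned. The step from 18 to 20 is justified by the other symptoms; no withdrawal rate is given.

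**Reproducing the plan's figure.** n per group = 2 × (1.96 + 0.8416)² × 1.58² / 1.5² = 17.4, rounded up to 18. This matches. The t-based solution is 18.4, or 19. With 20 v 20, t-test power is 83%.

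**Loss alone, unrelated to outcome.** With 20 in Group B and 18, 16 or 14 controls left, t-test power is 81%, 79% or 75%. With 17 left it is 80%, and the estimate stays at 1.50.

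**Loss related to outcome: assumptions.** 3 of 20 controls (15%) withdraw, and need for care has correlation r with a poor result. Neither figure is in the protocol.

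*Day 21 outcomes.* The expected mean of the three most extreme of 20 standard normal values is about 1.47. Removing them moves the mean of the other 17 by 3 × 1.47 / 17 = 0.259 SD, so the shift is r × 0.259 SD. For r = 0.2, 0.5 and 1.0 this is 0.05, 0.13 and 0.26 SD. If six leave, the multiplier is about 0.48 SD.

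*ESAS, all data of withdrawn controls dropped.* Expected estimate = 1.5 − r × 0.259 × 1.58 = 1.5 − 0.409r. Power is from simulated two-sided 5% t-tests.

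| Correlation r | Estimate, 3 lost | Power, 3 lost | Estimate, 6 lost | Power, 6 lost |
|---|---|---|---|---|
| 0.2 | 1.42 | 75% | 1.35 | 67% |
| 0.5 | 1.30 | 69% | 1.12 | 53% |
| 1.0 | 1.09 | 59% | 0.75 | 32% |

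If selection runs the other way, so that the best-changing controls leave, the bias favours the intervention. With no true effect and three lost, favourable false positives are about 3.5%, 6% and 14% for r = 0.2, 0.5 and 1.0, instead of 2.5%.

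*ESAS, pairs before withdrawal kept.* Pairs are kept up to session 2, 4 or 6, change is stable over sessions, within-patient correlation is 0.3 to 0.7, and need correlates 0.5 or 1.0 with the patient's overall change. The estimate is then 1.49 to 1.51 and power 82% to 84%, so there is almost no bias. If exit instead follows two poor visits, the kept pairs over-represent the poor visits: the estimate rises to 1.50 to 1.68, and favourable false positives under no effect are 2.6% to 4.2%.

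**Cost of keeping these patients in.** If the three controls gain half of the 1.5-point effect, the as-randomised estimate is 1.5 − (3/20) × 0.75 = 1.39, with power 77%. If they gain all of it, 1.5 − (3/20) × 1.5 = 1.28, with power 68%.

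**The case against.** The strongest reply is that the harm to the primary outcome rests on a gap that a statistical analysis plan would normally fill. The large ESAS biases arise only if earlier pairs are thrown away, which the protocol does not say; if they are kept and change is stable, the bias nearly vanishes. That stands, and the whole-deletion figures should be read as conditional. It does not reach the assessments that are never made after withdrawal.

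Second, the withdrawal rate, the correlations and the link to symptoms are all assumed. A correlation of 1.0 is an extreme bound, and the 14% false-positive figure needs that bound together with full deletion and withdrawal of the best-changing controls. This also stands: the rule is certain, its size is not.

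Third, retention can cost as much as the defect for ESAS. Full benefit in three controls gives 1.28 points and 68% power, about the same as full deletion at r = 0.5, and it answers an as-randomised question rather than recovering the undiluted contrast. That is true. But once the data exist, the analysis without these patients can still be run; under the present rule the as-randomised analysis cannot.

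Two smaller points. Only section 3.6.1 names both groups in words. For the other instruments that is the natural reading, and nothing limits them to Group B. The discomfort clause in section 5.1 could remove patients from either arm, but it is not a matching need-based exit.

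**Conclusion.** The concern holds and should be fixed. As written, the rule produces control-only loss after randomisation, plausibly related to symptoms. It falls most clearly on the Day 21 or discharge outcomes, to which a control withdrawn earlier contributes nothing. Under the assumed 15% withdrawal, the control mean there shifts by up to 0.26 SD. For ESAS the effect runs from negligible (earlier pairs kept, stable change) to an estimate of 1.09 instead of 1.5 (all data dropped, perfect correlation). Frequency and direction cannot be known from the protocol. What is certain is that the missing assessments cannot be recovered afterwards.

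**What to change.** Leave the decision to give the care as it is. In section 3.5, replace the clause that ends participation with text to this effect:

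> The date and content of that care are recorded. The patient stays in the study and completes the ESAS before and after the remaining scheduled control visits (not around the practice sessions) and the Day 21 or discharge questionnaires.

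Add to section 3.7:

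> Patients are analysed in the group to which they were randomised, using all ESAS pairs collected at scheduled visits. A sensitivity analysis excludes control ESAS pairs recorded after the first such care.

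Report how many controls received the care, and when.

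The cost is one sentence changed in 3.5 and two added in 3.7. The visits and REDCap forms are already scheduled, though some controls would have control visits alongside practice sessions, which needs coordination. The statistical cost is the dilution shown above. The sensitivity analysis shows how far it matters for ESAS; it does not cover the Day 21 outcomes, where values from these controls would follow receipt of the care and should be described as such.
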